**Table 11: Simulated Probability of Early Stopping under Assumed ORR**

Interim Time Point (Enrollment at N =)	10	20	30	43	Futility at First Three Looks	Futility at End of Study	Efficacy at End of Study	Average Overall Sample Size 	
Stopping Boundary (No. of Responders)	0	1	3	6					
Assumed True Underlying ORR	0.05	0.60	0.19	0.16	0.05	0.95	1.00	0.00	11
	0.10	0.35	0.13	0.21	0.19	0.69	0.88	0.12	22
	0.15	0.20	0.07	0.13	0.19	0.40	0.59	0.41	32
	0.20	0.11	0.03	0.06	0.10	0.20	0.30	0.70	38
	0.25	0.06	0.01	0.02	0.03	0.09	0.12	0.88	41
	0.30	0.03	0.00	0.01	0.01	0.04	0.04	0.96	42

ORR = Objective Response Rate, N = Sample size; No. = Number

Without considering newly enrolled participants while the interim evaluation is ongoing.

As can be seen from the above table, the probabilities to stop for futility early if true ORR is either 5% or 10% are approximately 100% and 88%, respectively. The probabilities to stop for futility when true ORR is either 25% or 30% are approximately 12% and 4%, respectively. For various criteria to claim efficacy, the exact 95% CI for different corresponding observed ORR are listed in [Table 12](#). For example, if the total sample size is 20 at the second interim evaluation, the lower bound of the 95% CI will be 27.2% if the observed ORR is 50%. When the total sample size is 30 or higher and the observed ORR is 50%, the lower bound of the 95% CI will be  $\geq 31.3\%$ .

**Table 12: Exact 95% CI Given Observed ORR**

Minimum ORR to Claim Efficacy	Sample Size	Observed No. of Responders	Observed ORR (%)	95% Confidence Interval	
				Lower Bound	Upper Bound
0.25	10	3	30.0	6.7	65.3
	20	5	25.0	8.7	49.1
	30	8	26.7	12.3	45.9
	43	11	25.6	13.5	41.2
0.3	10	3	30.0	6.7	65.3
	20	6	30.0	11.9	54.3
	30	9	30.0	14.7	49.4
	43	13	30.2	17.2	46.1
0.5	10	5	50.0	18.7	81.3
	20	10	50.0	27.2	72.8
	30	15	50.0	31.3	68.7
	43	22	51.2	35.5	66.7

CI = Confidence Interval; ORR = Objective Response Rate

## 12.3. STATISTICAL ANALYSES

The statistical analysis plan (SAP) will describe the participant populations to be included in the analyses, and procedures for accounting for missing, unused, spurious data, and intercurrent events that may affect the assessment of the endpoints. This section is a summary of the planned statistical analyses of the primary and secondary endpoints.

### 12.3.1. Efficacy Analyses

All efficacy analyses will be based on treated participants. A brief description of the statistical method for efficacy analyses is summarized in [Table 13](#). Subset analyses for the primary endpoints may be performed for selected baseline characteristics. The details will be described in the SAP.

**Table 13: Statistical Method for Efficacy Analyses**

Primary Endpoint	Statistical analysis methods
Objective response rate, defined as the proportion of participants with CR + PR using RECIST v1.1	The response rate will be calculated, and the exact 95% CI will be provided. The proportion and 95% CI of participants with CR, PR, Stable Disease (SD), and Progressive disease (PD) will also be summarized and listed by visit.
Secondary Endpoint	Statistical analysis methods
Estimate of proportion of participants who have not progressed or died at 6 months of follow-up: PFS-6. Progression is defined by RECIST v1.1	The Kaplan-Meier (K-M) method will be used to estimate PFS-6.
Estimate the 2-year overall survival, defined as the proportion of participants who have not died after 2 years of follow-up after their first dose of nirogacestat	The K-M method will be used to estimate the distribution of overall survival
Change from baseline in FOSI	Change from baseline in the FOSI score and the individual responses will be summarized at each cycle, end of treatment, and the follow-up visit.
DoR, defined as the time from first assessment of response (CR + PR using RECIST v1.1) to first disease progression defined by RECIST v1.1 or death, whichever comes first	The K-M method will be used to estimate the distribution of the duration of response including median.
Exploratory Endpoint	Statistical analysis methods
Exploratory endpoint statistical analysis method will be described in the SAP.	

CI = Confidence interval; CR = Complete response; FOSI = Functional Assessment of Cancer Therapy – Ovarian Symptom Index; K-M = Kaplan-Meier; ORR = Objective Response Rate; PFS = Progression-Free Survival; PR = Partial Response; RECIST v1.1 = Response Evaluation Criteria In Solid Tumors version 1.1; SAP = Statistical Analysis Plan

### 12.3.2. Safety Analyses

All safety analyses will be performed on participants who received at least one dose of nirogacestat.

The safety and tolerability of nirogacestat will be evaluated by means of treatment-emergent AEs, physical examinations, and laboratory safety evaluations. Adverse Events will be graded by the Investigator according to the CTCAE v5.0 and coded using the Medical Dictionary for Regulatory Activities.

The focus on AE summaries will be on Treatment-Emergent AEs, those with initial onset or increasing in severity after the first dose of study treatment through 30 days after the last dose of study treatment. The number and percentage of participants who experienced an AE, SAE,

treatment related AE, and treatment related SAE will be summarized according to worst toxicity grades.

Summaries of clinical laboratory parameters will be summarized by study visit and overall, including absolute results and changes from baseline. Tables for the shift in CTCAE severity grade of laboratory data from baseline to the worst post-baseline value and from baseline to each visit will be presented.

Vital signs data will be summarized by study visit and overall using descriptive statistics. Summaries will be presented for the observed value, the change from baseline value, and the change from baseline to the worst post-baseline value during the treatment period.

The observed ECG values and change from baseline values, and the change from baseline to the worst post-baseline value during the treatment period will be summarized descriptively. The overall ECG assessments will be summarized categorically (normal, abnormal without clinical significance, and abnormal with clinical significance) as a shift table by study visit.

### **12.3.3. Other Analyses**

Pharmacokinetic, pharmacodynamic, and exploratory analyses will be described in the SAP (to be finalized before database lock). The population PK analysis and pharmacodynamic analyses will be presented separately from the main Clinical Study Report (CSR).

## **12.4. INTERIM ANALYSES**

No formal interim analysis is planned. This study will use a Bayesian approach of continuous monitoring for early futility stopping based on ORR, intended to limit the accrual of participants to an ineffective treatment ([Section 12.2](#)). The Statistical Analysis Plan will describe the planned continuous monitoring in greater detail.

### **12.4.1. Data Monitoring Committee**

There is no Data Monitoring Committee for this study.

## **13. SUPPORTING DOCUMENTATION AND OPERATIONAL CONSIDERATIONS**

### **APPENDIX 1. REGULATORY, ETHICAL, AND STUDY OVERSIGHT CONSIDERATIONS**

#### **A1-1. REGULATORY AND ETHICAL CONSIDERATIONS**

This study will be conducted in accordance with the protocol and with the following:

- Consensus ethical principles derived from international guidelines including the Declaration of Helsinki and Council for International Organizations of Medical Sciences (CIOMS) International Ethical Guidelines
- Applicable International Council for Harmonisation (ICH) Good Clinical Practice (GCP) Guidelines
- Regulation (EU) no. 563/2014
- Applicable laws and regulations

The protocol, protocol amendments, Informed Consent Form (ICF), Investigator Brochure, and other relevant documents (e.g., advertisements) must be submitted to an Institutional Review Board (IRB)/Independent Ethics Committee (IEC) by the Investigator and reviewed and approved by the IRB/IEC before the study is initiated.

Any substantial modifications/amendments to the protocol will require competent authority and IRB/IEC approval before implementation of changes made to the study design, except for changes necessary to eliminate an immediate hazard to study participants.

The Investigator will be responsible for the following:

- Providing written summaries of the status of the study to the IRB/IEC annually or more frequently in accordance with the requirements, policies, and procedures established by the IRB/IEC;
- Notifying the IRB/IEC of Serious Adverse Events (SAEs) or other significant safety findings as required by IRB/IEC procedures; and
- Providing oversight of the conduct of the study at the site and adherence to requirements of 21 Code of Federal Regulations (CFR), ICH guidelines, the IRB/IEC, European regulation 536/2014 for clinical studies (if applicable), and all other applicable local regulations

#### **A1-2. FINANCIAL DISCLOSURE**

Principal Investigators and Sub-Investigators will provide the Sponsor with sufficient, accurate financial information as requested to allow the Sponsor to submit complete and accurate financial certification or disclosure statements to the appropriate regulatory authorities.

Investigators are responsible for providing information on financial interests during the course of the study and for 1 year after completion of the study.

### **A1-3. INFORMED CONSENT PROCESS**

The Investigator or his/her representative will explain the nature of the study to the participant or her legally authorized representative and answer all questions regarding the study.

Participants must be informed that their participation is voluntary. Participants will be required to sign a statement of informed consent that meets the requirements of 21 CFR 50, local regulations, ICH guidelines, Health Insurance Portability and Accountability Act (HIPAA) requirements, where applicable, and the IRB/IEC or study center.

The medical record must include a statement that written informed consent was obtained before the participant was enrolled in the study and the date/time the written consent was obtained. The authorized person obtaining the informed consent must also sign the Informed Consent Form (ICF).

Participants must be re-consented to the most current version of the ICF(s), as per IRB/IEC guidance, during their participation in the study.

A copy of the ICF(s) must be provided to the participant or the participant's legally authorized representative.

### **A1-4. DATA PROTECTION**

Participants will be assigned a unique identifier by the Sponsor. Any participant records or datasets that are transferred to the Sponsor will contain the identifier only; participant names or any information which would make the participant identifiable will not be transferred.

Participants must be informed that their personal study-related data will be used by the Sponsor in accordance with local data protection law. The level of disclosure must also be explained to the participant.

Participants must be informed that their medical records may be examined by Quality Assurance auditors or other authorized personnel appointed by the Sponsor, by appropriate IRB/IEC members, and by inspectors from regulatory authorities.

Sponsor maintains robust technical security measures in relation to its systems and by implementing security procedures concerning the handling of sensitive information. The Sponsor maintains data incident response policies governing how to respond in the event of unauthorized access, use, or disclosure of sponsor information or systems each a "Data Issue". Sponsor, in consultation with the DPO, will assess the Data Issue as soon as possible and will undertake mitigation measures to contain the Data Issue to prevent further impact, including shutting down affected applications or third-party connections, reconfiguring firewalls, changing computer access codes, and modifying physical access controls. Sponsor will determine if an intruder has exported or deleted any information. Sponsor may use the FRM-0128, Data Incident Reporting Form to document the Data Issue and share relevant documentation with the DPO as it pertains

to Data Issues affecting EEA, Switzerland or UK Data Subjects. Sponsor will provide notice of the Data Issue to impacted data subjects in accordance with Applicable Laws.

## **A1-5. DATA QUALITY ASSURANCE**

All participant data relating to the study will be entered into the electronic case report forms (eCRFs) unless transmitted to the Sponsor or designee electronically (e.g., laboratory data). The Investigator is responsible for verifying that data entries are accurate and correct by electronically signing the eCRF.

The Investigator must maintain accurate documentation (source data) that supports the information entered in the eCRF.

The Investigator must permit study-related monitoring, audits, IRB/IEC review, and regulatory agency inspections and provide direct access to source data documents.

Monitoring details describing strategy methods, responsibilities, and requirements, including handling of non-compliance issues and monitoring techniques (central, remote, or onsite monitoring) will be indicated in the monitoring plan to ensure the protocol and GCP is followed.

The Sponsor or designee is responsible for the data management of this study including quality checking of the data.

The sponsor assumes accountability for actions delegated to other individuals (e.g., Contract Research Organizations).

Study monitors will perform ongoing source data verification to confirm that data entered into the eCRF by authorized site personnel are accurate, complete, and verifiable from source documents; that the safety and rights of participants are being protected; and that the study is being conducted in accordance with the currently approved protocol and any other study agreements, ICH GCP, and all applicable regulatory requirements.

Records and documents, including signed ICFs, pertaining to the conduct of this study must be retained by the investigator according to specifications in the ICH guidelines, local regulations, or as specified in the clinical trial agreement, whichever is longer. No records may be destroyed during the retention period without the written approval of the sponsor. No records may be transferred to another location or party without written notification to the Sponsor.

## **A1-6. SOURCE DOCUMENTS**

Source documents provide evidence for the existence of the participant and substantiate the integrity of the data collected. Source documents are filed at the investigator's site.

Data entered in the eCRF that are transcribed from source documents must be consistent with the source documents or the discrepancies must be explained. The investigator may need to request previous medical records or transfer records, depending on the study. Also, current medical records must be available.

Investigators will maintain records separate from the eCRFs in the form of clinical charts, medical records, original laboratory, radiology and pathology reports, pharmacy records, etc. The investigator will document in the clinic chart or medical record the date on which the participant signed informed consent prior to participation in the study. Source documents must completely reflect the nature and extent of the participant's medical care and must be available for source document verification against entries in the eCRFs when the sponsor's monitor visits the site. In order to meet data integrity requirements, source documentation should be attributable, legible, contemporaneous, accurate, available/accessible, original, complete and credible. All information obtained from these documents will be kept in strict confidentiality. Definition of what constitutes source data can be found in the study reference manual.

#### **A1-7. STUDY AND SITE CLOSURE**

The Sponsor (or designee) reserves the right to close the study site or terminate the study at any time for any reason at the sole discretion of the Sponsor. Study sites will be closed upon study completion. A study site is considered closed when all required documents and study supplies have been collected and a study-site closure visit has been performed.

Study-site closure prior to completion of the study should be avoided. The Investigator and Sponsor will agree to the circumstances that could cause early study-site closure.

The Investigator may initiate study-site closure at any time, provided there is reasonable cause and sufficient notice is given in advance of the intended termination.

Conditions that may warrant early study site closure but are not limited to:

- The discovery of an unexpected, serious, or unacceptable risk to participants participating in the study;
- A negative change in the risk/benefit assessment;
- Failure of the investigator to comply with the protocol, the requirements of the IRB/IEC or local health authorities, the Sponsor's procedures, or GCP guidelines
- Inadequate recruitment of participants by the Investigator; or
- The decision on the part of the Sponsor to suspend or discontinue nirogacestat development.

#### **A1-8. PUBLICATION POLICY**

Following completion of the trial, the data may be considered for publication in a scientific journal or for reporting at a scientific meeting. Each Investigator is obligated to keep data pertaining to the trial confidential. The Investigator must consult with the Sponsor before any trial data are submitted for publication. The Sponsor reserves the right to deny publication rights until mutual agreement on the content, format, interpretation of data in the manuscript, and journal selected for publication are achieved.

## **APPENDIX 2. PROHIBITED CONCOMITANT MEDICATIONS**

A listing of cytochrome P450 (CYP3A4) inhibitors/inducers, P-glycoprotein (P-pg) inhibitors/inducers, protein pump inhibitors (PPIs), and H2 receptor antagonist will be provided in the Study Reference Manual. Contact the Medical Monitor for questions.

### **APPENDIX 3. RECIST CRITERIA V1.1**

For full guidelines, see RECIST Criteria v1.1 ([Eisenhauer 2009](#))

#### **Categorizing lesions at Baseline:**

- Only participants with measurable disease (i.e., at least one measurable lesion) at Screening are included.

**Measurable lesion** – Lesion that can be accurately measured in at least one dimension (longest diameter [LD]) in the plane of measurement is to be recorded) and with longest diameter at least twice the slice thickness and at least 10 mm when assessed by computed tomography (CT) or magnetic resonance imaging (MRI)

- Measurable disease will be assessed by CT or MRI.
- The same method of assessment (CT or MRI) and the same technique will be used to characterize each identified and reported lesion at Screening and during follow-up.
- Target Lesions - up to 2 lesions per organ and 5 lesions in total, representative of all involved organs at Baseline.
- Non-target Lesion - All other lesions (or sites of disease) will be identified as non-target lesions and should also be recorded at Baseline. Measurements of these lesions are not required, but the presence or absence of each should be noted throughout follow-up.

#### **Methods of Measurement**

CT or MRI must be used to measure target lesions selected for response assessment. Conventional CT and MRI will be performed with cuts of 10 mm or less in slice thickness contiguously.

#### **Recording Tumor Assessments**

All sites of disease must be assessed at Screening. Screening assessment must be done within 28 days of starting study treatment. For an adequate screening assessment, all required scans must be done within 28 days prior to first dose of study treatment and all disease must be documented appropriately.

At follow-up, disease site must be assessed using the method (CT or MRI) and same technique as screening, including consistent administration of contrast (CT only) and timing of scanning. If a change needs to be made the case must be discussed with the Sponsor.

Unequivocal new lesions will be recorded at follow-up time points. Measurement of new lesions is not required. If a new lesion is equivocal, for example because of its small size, continued therapy and follow-up evaluation will clarify if it represents truly new disease. If repeat scans confirm there is definitely a new lesion, then progression should be declared using the date of the initial scan.

### Response Criteria: Evaluation of target lesions

Complete Response (CR):	Disappearance of all target lesions.
Partial Response (PR):	At least a 30% decrease in the sum of the LD of target lesions, taking as reference the baseline sum of LD.
Progressive Disease (PD):	At least a 20% increase in the sum of the LD of target lesions, taking as reference the smallest sum of LD recorded since the treatment started or the appearance of one or more unequivocal new lesions. In addition to the relative increase of 20%, the sum must also demonstrate an absolute increase of at least 5 mm.
Stable Disease (SD):	Neither sufficient shrinkage to qualify for PR nor sufficient increase to qualify for PD, taking as reference the smallest sum LD since the treatment started.

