## 5. OBJECTIVES AND ENDPOINTS

**Table 4: Objectives and Endpoints**

Objectives	Endpoints
Primary Objective	Primary Endpoint
To determine the anti-tumor activity of nirogacestat in adult participants with relapsed/refractory OvGCT	Objective response rate (ORR) defined as the proportion of participants with Complete Response (CR) + Partial Response (PR) using RECIST v1.1 criteria
Secondary Objectives	Secondary Endpoints
To determine if nirogacestat delays progression or death in OvGCT	Estimate of proportion of participants who have not progressed or died at 6 months of follow-up: PFS-6. Progression is defined by RECIST v1.1
To describe overall survival in participants treated with nirogacestat	Estimate of 2-year overall survival, defined as the proportion of participants who have not died after 2 years of follow-up after their first dose of nirogacestat
To determine the effect of nirogacestat on ovarian cancer symptoms measured by Functional Assessment of Cancer Therapy – Ovarian Symptom Index (FOSI)	Change from baseline in FOSI
To determine the duration of response	Duration of response (DoR), defined as the time from first assessment of response (CR + PR using RECIST v1.1) to first disease progression defined by RECIST v1.1 or death, whichever comes first
To determine the pharmacokinetics (PK) of nirogacestat	Serum concentrations of nirogacestat will be measured to evaluate system exposures ( $C_{\max}$ , $C_{\text{trough}}$ and other PK parameters as data allow)
Safety Objectives	Safety Endpoints
To characterize the safety and tolerability of nirogacestat at a dose of 150 mg BID in adult participants with relapsed/refractory OvGCT	Key safety endpoints will include incidence of treatment emergent Adverse Events (TEAEs), changes in clinical laboratory parameters, vital signs, physician examination findings, and electrocardiograms (ECGs). Tolerability will be assessed according to toxicities graded by National Cancer Institute Common Terminology Criteria for Adverse Events (CTCAE) v5.0
Exploratory Objectives	Exploratory Endpoints
To detect FOXL2 C134W mutation as well as other genomic alterations and correlate these with response	Evaluate NGS status in baseline tumor tissue

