### Evaluation of best overall response

The best overall response is the best response recorded from the start of the study treatment until disease progression/recurrence (taking as reference for PD the smallest measurements recorded since the start of study treatment). The participant's best response assignment will depend on the achievement of both measurement and confirmation criteria (defined below).

Target Lesions	Nontarget Lesions	New Lesions	Overall Response
CR	CR	No	CR
CR	Non-CR/non-PD	No	PR
CR	Not evaluated	No	PR
PR	Non-PD or not all evaluated	No	PR
SD	Non-PD or not all evaluated	No	SD
Not all evaluated	Non-PD	No	NE
PD	Any	Yes or No	PD
Any	PD	Yes or No	PD
Any	Any	Yes	PD

CR=Complete Response; NE=Not Evaluable; PD=Progressive Disease; PR=Partial Response; SD=Stable Disease.

Participants with a global deterioration of health status requiring discontinuation of study treatment without objective evidence of disease progression at that time will be classified as

having “symptomatic deterioration”. Every effort should be made to document the objective progression even after discontinuation of treatment.

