1.3. Study Design

This is a multi-center, single-arm, Phase 2 open label treatment study to determine the efficacy, safety, tolerability, and pharmacokinetics of nirogacestat in adult participants with recurrent OvGCT. Participants must have received at least one prior course of systemic therapy for OvGCT and have measurable disease by RECIST v1.1 to meet the eligibility criteria.

The Schedule of Assessments (SoA) is in protocol Section 1.3, Table 2. Participants will be screened up to 28 days prior to the first dose of study treatment (nirogacestat) and full eligibility will be based on the inclusion and exclusion criteria (Protocol Section 7.1 and 7.2).

Participants will administer 150 mg (3 × 50 mg tablets) of study treatment BID, continuously in 28-day cycles. Participants will remain on study treatment until death, disease progression (unless the participants meet criteria for continued treatment), discontinuation of study treatment for any reason, the study is stopped by the Sponsor for any reason, or participant qualifies for Sponsor's Compassionate Use Program.

All scans will be performed and read locally by the site's radiologist for Tumor assessment as per RECIST v1.1. Same modality used at Screening must be used at each subsequent imaging visits. Baseline scan is defined as scans performed prior to first dose of study treatment. On treatment scans are performed every 8 weeks (C3D1, C5D1, C7D1) for the first 6 months and then every 12 weeks (C10D1, C13D1, etc.) thereafter. Scans may be performed (-) 7 days prior to the visit.

The final 2-year survival check-in will occur approximately 2 years after the first dose of study treatment. If participant discontinues from study treatment prior to the 2-year check-in, quarterly telephone or email contact following EOT is required until the 2-year survival data point has

been collected. In addition, collection of subsequent anticancer therapy after nirogacestat and overall response to this therapy will be recorded. Only information about the subsequent therapy used directly after nirogacestat is required along with the final survival outcome at the 2-year check point.

Participants who discontinue study treatment early for any reason should return to the clinic for an End of Treatment (EOT) visit within 7 days after the Investigator determines study treatment will no longer be used and then again for a safety Follow-up (FUP) visit 30 days (+7 days) after the last dose of study treatment.

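### The printed progression reference leaves out the pre-dose baseline scan; applied literally, it can date target-lesion progression late and, on some growth paths, change PFS-6

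*Protocol*

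**What the plan says.** In the target-lesion table of Protocol Appendix 3, partial response is judged "taking as reference the baseline sum of LD". Progression is judged differently: a 20% increase, "taking as reference the smallest sum of LD recorded since the treatment started or the appearance of one or more unequivocal new lesions", and in addition "the sum must also demonstrate an absolute increase of at least 5 mm". The stable-disease row uses the same since-treatment reference. The best-response paragraph repeats it, "taking as reference for PD the smallest measurements recorded since the start of study treatment", as do the paragraphs on duration of response and of stable disease. SAP 8.1 carries the same text.

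The baseline scan lies outside that period. Appendix 3 requires that "all required scans must be done within 28 days prior to first dose of study treatment", and SAP 1.3 states: "Baseline scan is defined as scans performed prior to first dose of study treatment". No section of either document adds the baseline sum to the PD or SD reference.

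Two other features bear on how the text is read. Both appendices open by deferring to the guideline ("For full guidelines, see RECIST Criteria v1.1"), and the PFS-6 endpoint says "Progression is defined by RECIST v1.1". On the other hand, Protocol 11.1.1 sends the reader to Appendix 3 for the response definitions, and SAP 3.1 sends the reader to SAP 8.1 for the details. All reads are local, by each site's radiologist.

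**The concern.** Read as printed, C3D1 is the first sum that can enter the PD reference, so growth between the pre-dose scan and C3D1 never counts. A target-lesion increase cannot be called at C3D1 at all. At later scans the tumor is compared with an already enlarged C3D1 sum.

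A reader who includes baseline and one who does not can therefore assign different progression dates to the same scans. The documents describe no central read that would settle the difference. First progression drives PFS, PFS-6 and the split between SD and PD as best response, and it starts the clock for PFS on continued treatment. Protocol Section 9 on treatment after initial progression is keyed to the same finding.

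**Working it through.** No target, power or sample-size figure in the plan depends on the PD reference, so there is no stated number to reproduce. The check applies both readings to the planned scan days.

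**Inputs.** Scan days 57, 113, 169, 253 and 337 for C3D1, C5D1, C7D1, C10D1 and C13D1 (Protocol 1.3, SAP 1.3). Month length 30.4375 days (SAP 4.1), so six months is 6 × 30.4375 = 182.6 days. Progression is dated at the earliest scan that shows it (SAP Table 3). PD needs at least +20% and at least +5 mm. Growth rates are assumptions; the documents give none.

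**When the readings differ.** If any earlier on-treatment sum is at or below baseline, both references are equal. They differ only while every earlier on-treatment sum exceeds baseline.

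**Steady exponential growth g per 8 weeks, baseline scan at Day 1, baseline sum 100 mm.** In 8-week units the scans fall at 1, 2, 3, 4.5 and 6. With baseline included, PD is the first scan with (1+g)^t ≥ 1.2. As printed, PD is the first scan after C3D1 with (1+g)^(t−1) ≥ 1.2.

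| g | Sums on Days 57, 113, 169, 253 (mm) | PD day, baseline included | PD day, as printed | PFS-6 status |
|---|---|---|---|---|
| 4% | 104.0, 108.2, 112.5, 119.3 | 337 | 337 | same |
| 5% | 105.0, 110.2, 115.8, 124.6 | 253 | 337 | same (event-free) |
| 8% | 108.0, 116.6, 126.0, 141.4 | 169 | 253 | event becomes event-free |
| 12% | 112.0, 125.4, 140.5, 166.5 | 113 | 169 | same (event) |
| 25% | 125.0, 156.2, 195.3, 273.0 | 57 | 113 | same (event) |

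**Band that changes PFS-6.** C3D1, C5D1 and C7D1 all fall before Day 182.6, so moves from Day 57 to 113 or from Day 113 to 169 leave PFS-6 alone. A change needs PD by Day 169 with baseline included, (1+g)^3 ≥ 1.2, but no PD by Day 169 as printed, (1+g)^2 < 1.2. That gives 1.2^(1/3) − 1 = 6.3% up to 1.2^(1/2) − 1 = 9.5%.

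**Linear growth.** 1+3g ≥ 1.2 gives 6.7%. (1+3g)/(1+g) < 1.2 gives g < 0.2/1.8 = 11.1%. Between 10% and 11.1%, PD with baseline included falls on Day 113 (1+2g ≥ 1.2) and as printed on Day 253, which is two scans later.

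**Baseline timing and the 5 mm rule.** With the baseline scan at Day 1 or 28 days before dosing, and baseline sums of 20 to 100 mm, the bands span about 5.4% to 10.7% (exponential) and 5.8% to 12.5% (linear). An early baseline scan can also give a two-scan delay. At g = 8% with a scan 28 days before dosing, Day 113 is 2.5 units from baseline and 1.08^2.5 = 1.21, so PD is Day 113 with baseline included. As printed, 1.08^2 = 1.17 at Day 169, so PD is Day 253.

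**Size per participant.** 1/53 = 1.9 points (53 enrolled, SAP 5.8 and 6) or 1/43 = 2.3 points (planned number), before censoring enters the Kaplan-Meier estimate.

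**The case against.** The strongest reply is that the appendix is an extract and RECIST v1.1 governs. PFS-6, DoR and SAP Table 3 all define progression by RECIST v1.1, and the SAP 3.1 pointer to SAP 8.1 sits under ORR, not PFS-6. SAP 5.3 also accepts stable disease from 7 weeks, which is the C3D1 scan, where baseline is the only earlier measurement. On this view the literal reading defeats itself and nobody would apply it.

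Most of that stands. It shows that baseline was probably intended, and nothing in the documents shows that any site leaves it out. It does not remove the defect. Protocol 11.1.1 and SAP 3.1 present these appendices as the working definitions, the reads are local, and the printed reference is specific, repeated and contrasted with the PR row, which does name baseline.

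A reader might go further and infer that progression is being called one scan late throughout and that PFS-6 is inflated. The documents do not support that. The effect depends on the text being applied literally. The delay can be none (4% growth), one scan or two. Only calls that slip past C7D1 reach the six-month landmark. A reader might also see a contradiction with SAP 5.3, which lists PD as a best response. There is none, because new lesions and non-target progression can still produce PD at C3D1.

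**Conclusion.** The point holds as a wording error in both documents with a conditional effect. Under the printed text, target-lesion growth without initial shrinkage is usually dated one scan late: 8 weeks up to C7D1, 12 weeks after it. PFS-6 changes only when progression that would be called by C7D1, in the simplest case first at C7D1, moves to C10D1. That corresponds to roughly 5% to 12.5% growth per 8 weeks across the cases examined.

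The direction is always toward later progression and higher PFS-6. The total cannot be stated, because neither the growth rates nor the number of participants on such paths is given, and that number may be zero. ORR is essentially unaffected, since PR uses the baseline sum. Progression by new or non-target lesions, deaths, and regrowth from a nadir below baseline are likewise unaffected, so DoR barely moves. PFS-6 is a descriptive secondary endpoint with no test attached, which limits the consequence but does not make two progression dates for the same scans acceptable.

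**What to change.** For the endpoint definitions, state in the PD and SD rows and in the best-response and duration paragraphs of Protocol Appendix 3 and SAP 8.1 that the reference is the smallest sum on study, including the baseline sum. Reconcile that wording with the RECIST v1.1 guideline both documents cite; its text is not in the documents and was not checked here.

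In the SAP, derive target-lesion PD for PFS, PFS-6 and best overall response from the recorded sums on that basis, as a programmed check. List every participant whose site-reported PD date differs. The listing also shows whether any site used the literal reading.

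Protocol Section 9 on continuing treatment after progression refers to the same finding; any effect there should be handled by reconciling the passages.

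The cost is a few words in two documents and one small programming check on target-lesion sums, which SAP 5.3.1 already plans to summarize. PFS-6 may come out slightly lower.
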